Prior to surgery, all consecutive patients scheduled for LVAD implantation will be screened for inclusion into the study. If the patient fulfills the inclusion criteria for the study, he/she will be approached and the study will be described. If the patient agrees to participate, he /she will be given written, informed consent for inclusion in the study. Baseline demographic and clinical characteristics of patients, echocardiographic parameters, hemodynamic data from right heart catheterization and blood samples will be collected. These procedures are a part of standard of care procedures, so the patients will not suffer any discomfort or additional cost due to the inclusion in the study. However, patients will be asked to provide additional blood samples for advanced hemostatic assays and panel reactive antibodies. Randomization is done intraoperatively as detailed later. In cases where the patient will not be eligible for inclusion into the study prior to randomization (e.g. if during the heart positioning the patient becomes hemodynamically unstable and the CPB will a priority have to be used), the additionally collected blood samples will be discarded. The operation is initiated by a standard procedure and all postoperative management will be completed according to institution protocols and standard of care medical guidelines.

Randomization will be done with the help of the REDCap (REDCap electronic data capture tools hosted at UTHealth) (36), a software program that contains a randomization module using stratified randomization (by type of LVAD therapy).

The primary hypothesis is that off-pump LVAD surgery compared with on-pump LVAD surgery reduces a composite outcome of right ventricular dysfunction, thrombotic complications and survival in the short term (30 days) and that these benefits are maintained at long term (1 year). The secondary hypothesis is that off-pump LVAD surgery compared with on-pump LVAD surgery reduces OHP leading to lower complement activation and reduced immune allosensitization in the short term (30 days) and at long term (1 year).

Inclusion criteria

- Adult (≥ 18 years of age)
- The patient has had a diagnosis of end stage heart failure, NYHA class III or IV HF for a minimum of 90 days prior to screening.
- The patient has guideline-directed medical therapy according to ACC/AHA/ESC HF guidelines
- The patient has an Interagency Registry for Mechanically Assisted Circulatory Support (INTERMACS) score of 1-3.

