the blood contacting surfaces of device inflow cannula or outflow conduit or grafts. This will be reported via direct visual inspection (documented by a photograph if available) on pump removal or by sending the pump back to manufacturer for evaluation. Any pump explanted for suspected device thrombosis will be sent back to manufacturer for analysis. All pump thrombosis events will be adjudicated by an independent committee, the Research Review Committee which is described below in the Data and Safety Monitoring Section.

- For patients who will **die in the hospital within 30 days**, the cause of death will be confirmed by postmortem examination performed by a pathologist who will be unaware of the study assignments.

Secondary Outcome Measures

1. Need for blood product transfusion within 48-hours post LVAD implantation
2. Operative safety outcomes: incidence of 30-day mortality (from the day of surgery to 30 days [+/- 3 days]), chest tube output in the first post-operative 24 hours, rate of post-operative re-exploration for bleeding
3. Incidence of allosensitization at 30-days, 6-months and 12-months post-LVAD implantation. Allosensitization is defined as calculated panel reactive antibody (cPRA) > 10%.
4. Readmission for heart failure (follow-up 1 year)
5. OHP, overall coagulation potential and overall fibrinolytic potential in the perioperative period
6. Major bleeding defined as an episode of suspected internal or external bleeding that results in one or more of the following: death, re-operation, hospitalization, transfusion of red blood cells according to INTERMACS definition.

Other Outcome Measures

1. Duration of surgery (skin incision to skin closure)
2. Duration of postoperative mechanical ventilation (length of time from intubation until patient is extubated)
3. Length of ICU stay (length of time from ICU admission from surgery until ICU discharge)
4. Length of hospital stay (length of time from surgery to hospital discharge)
5. Incidence of renal dysfunction defined by INTERMACS criteria
6. Incidence of 30-day mortality (from the day of surgery to 30 days [+/- 3 days])
7. Incidence of post-operative mortality within 6 months and 1 year

8. Device-related complications totaled at 30-days, 6-months and 12-months post-LVAD implantation.
9. Duration and amount of intraoperative and postoperative inhaled nitric oxide use

COLLECTION OF BASIC DATA/PATIENT CHARACTERISTICS

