To evaluate the role of CPB on hemostatic and fibrinolytic parameters, we will make sure that the perioperative level of heparinization will be comparable between groups.

All patients will be postoperatively treated with 81mg aspirin daily and coumadin with a target international normalized ratio range of 2.0–2.5. Data on the use of antithrombotic therapy will be recorded at baseline and at each follow-up appointment. Time-in-Therapeutic Range (TTR) will be calculated using the Rosendaal method as a measure of quality of anticoagulation dose management (42).

Use of tranexamic acid

Tranexamic acid is a well-documented fibrinolytic inhibitor. The medical team will be advised to use always the same dose of tranexamic acid (if the patient's condition will allow it) in the perioperative period as it has an effect on overall fibrinolytic potential.

SELECTION OF SURGEONS

All surgical procedures will be performed by an "experienced" cardiac surgeon with more than 5 years of practice in cardiac surgery after residency training and has performed more than 100 LVAD implantations. Primary surgeons have experience with both techniques (on-pump and off-pump LVAD implantation). All procedures will be done under the supervision of an "expert" cardiac surgeon ([name]/PI of this protocol) who has more than 30 years of experience in advanced and complex cases of cardiac surgery, has performed more than 500 LVAD implantations, and is very experienced with both techniques (on-pump and off-pump LVAD implantation). Residents and fellows will not be eligible to participate as primary surgeons in the trial.

BLOOD COLLECTION AND PREPARATION

For research purposes, two additional vials of blood will be collected at the same time that standard of care blood draws are done. The timepoints for the research blood draws will be at baseline (within 48 hours of surgery), within 24-48 hours post-operation (but before discharge), 30 days, 6 months and 1 year. For the follow-up blood draws (+/- 5 days is acceptable).

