Preparation of buffy coat: Buffy coat will be removed after the first spinning of the centrifuge and decanted into Eppendorf tubes. The remaining packed RBCs in tubes will be stored for later (storage at -80°C).

DETERMINATION OF ALLOANTIBODIES

The measurement and assessment of alloantibodies is now a standard of care test performed on patients scheduled for LVAD surgery. A single-bead antigen assay on the Luminex platform (One Lambda Inc., Canoga Park, CA) is used at the institution. Mean fluorescence intensity (MFI) >4,000 is considered the threshold of clinical significance. Whenever the alloantibodies and panel reactive antibody status (PRAs) are measured, the data will be transferred from the medical record to the case report forms.

Calculated PRA (cPRA) values will be obtained using the United Network of Organ Sharing cPRA calculator. Sensitization will be defined as cPRA >10%. LVAD-associated sensitization will be defined as cPRA >10% documented after LVAD implantation in patients with cPRA <10% before LVAD implantation.

STATISTICAL METHODS

We calculated a sample size of 140 patients (70 in each arm), which will provide 80% power to detect a 30% relative risk reduction for the composite primary outcome at 30 days. The intention-to-treat principle, in which all participants will be included in their assigned treatment groups regardless of actual surgical procedure performed, will guide all analyses.

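### The plan conflicts on where post-implant cPRA comes from: extra research blood is scheduled, but results are taken from the chart and no assay is ordered on the scheduled samples

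*Combined protocol and SAP*

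**What the plan says.** All references are to the combined protocol and SAP.

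- **Secondary Outcome Measures**, item 3: "Incidence of allosensitization at 30-days, 6-months and 12-months post-LVAD implantation", with sensitization set at a cPRA above 10%. The secondary hypothesis in Study Design and Patients also names allosensitization, at 30 days and 1 year.
- **Study Design and Patients**: "patients will be asked to provide additional blood samples for advanced hemostatic assays and panel reactive antibodies".
- **Blood Collection and Preparation**: "The timepoints for the research blood draws will be at baseline (within 48 hours of surgery), within 24-48 hours post-operation (but before discharge), 30 days". The list continues to 6 months and 1 year, with 5 days either way at follow-up. Collection of Longitudinal Data confirms that research draws take place at the follow-up appointments.
- **Determination of Alloantibodies**: "The measurement and assessment of alloantibodies is now a standard of care test performed on patients scheduled for LVAD surgery". On the data source it says: "Whenever the alloantibodies and panel reactive antibody status (PRAs) are measured, the data will be transferred from the medical record". The section names one institutional single-antigen bead assay and an MFI threshold of 4,000. It gives no testing schedule after implant.
- **Laboratory parameters** (under Collection of Basic Data/Patient Characteristics): panel reactive antibodies are not in the list of routine tests taken before surgery and at the follow-up visits.
- **Statistical Methods**: analysis is by assigned group. Nothing says how a patient without a cPRA result is counted.

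**The concern.** An incidence at three fixed times needs a result for each patient at each time, obtained in the same way in both arms. The section that describes how alloantibodies are determined does not secure this. It takes over whatever results the medical record holds, and the only standard-of-care testing it describes is for patients awaiting surgery. A reader who follows it would have post-implant values where a clinician ordered the test and gaps elsewhere.

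Three things are at stake for this one secondary outcome:

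- **Completeness.** The number of patients with a value at each visit is not under the trial's control.
- **Comparability.** Expected Results and Importance of the Study anticipates lower use of blood products off-pump. If transfusion prompts clinicians to order the test, testing would follow arm. The design promises blinded outcome assessment, but no section blinds the clinicians who order this test.
- **Counting.** The definition of LVAD-associated sensitization asks for a raised value documented after implant, with no time point. A patient tested more often has more chances to meet it.

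**Working it through.** **1. Sections side by side.** The plan states no completeness or testing rate, so there is no figure to reproduce. The check is whether the sections agree.

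| Question | Study Design and Patients; Blood Collection and Preparation | Determination of Alloantibodies |
|---|---|---|
| Where does cPRA come from? | Extra research blood, taken partly for this purpose | Medical record |
| When? | Baseline, 24-48 hours, 30 days, 6 months, 1 year | Whenever measured; standard testing described for patients awaiting surgery |
| In whom? | All participants, regardless of arm | Those with a result on the chart |
| Is the assay ordered on the research sample? | Not stated | Not stated |

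The draws cover every time point of the outcome. The missing step is an instruction to run the assay on them. A scheduled draw is not a scheduled assay.

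**2. When would chart-dependent testing distort the comparison?**

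Inputs:
- True rate p = 0.22 in both arms. This is the sensitization figure quoted in the Background section on immunologic effects, used here for illustration.
- Testing probabilities ts (sensitized patients) and tn (non-sensitized patients). These are assumptions, because the documents give none.

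Formulas:
- Untested counted as negative: observed rate = p × ts
- Tested patients as denominator: observed rate = p × ts / [p × ts + (1 − p) × tn]

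*Case A. Testing unrelated to sensitization: 90% on-pump, 60% off-pump.*
- Untested as negative: 0.22 × 0.90 = 0.198 against 0.22 × 0.60 = 0.132. Relative risk 0.132 / 0.198 = 0.67.
- Among the tested: 22% against 22%. Relative risk 1.0.
- Range for untested as negative, with off-pump testing from 50% to 80%: 0.110 to 0.176 against 0.198, relative risk 0.56 to 0.89. Among the tested it stays at 1.0 throughout.

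*Case B. Selective testing on-pump only: 90% of sensitized and 60% of non-sensitized tested on-pump, 60% of all tested off-pump.*
- On-pump, among the tested: 0.198 / (0.198 + 0.78 × 0.60) = 0.198 / 0.666 = 29.7%.
- Off-pump, among the tested: 0.132 / (0.132 + 0.468) = 0.132 / 0.600 = 22.0%.
- False difference: 7.7 percentage points.

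*Case C. The same selective testing (90% and 60%) in both arms.*
- Among the tested: 29.7% against 29.7%. Both rates are inflated, with no difference between arms.

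A between-arm bias therefore needs one of two things: selective testing that differs by arm, or unequal testing combined with counting untested patients as negative.

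**3. Loss of information without any bias.** Take a true halving from 22% to 11% (an assumption), two-sided 5%, normal approximation: power = Φ{[d − 1.96 √(2 p̄(1 − p̄)/n)] / √[(p1(1 − p1) + p2(1 − p2))/n]}, with d = 0.11 and p̄ = 0.165.
- All 70 per arm tested: (0.11 − 0.1230) / 0.0620 = −0.21, power 42%.
- 60% tested, 42 per arm: (0.11 − 0.1588) / 0.0801 = −0.61, power 27%.

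**The case against.** The best defence is that the chart sentence is a data-transfer rule. It says where a result is copied from once it exists. It does not say that clinicians alone decide when to test. Read with the request for extra blood and the draw schedule, it could mean that every result, including those from scheduled draws, reaches the case report form. The absence of the test from the routine laboratory list is then weak evidence, because the plan treats this blood as additional to routine care. The institutional assay and its threshold are already named, and this is a single-centre trial. This stands to the extent that nobody can say the plan relies on the chart alone. It does not close the gap, because no section orders the assay on the scheduled samples or says how a missing result is handled.

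A reader might go further and infer that on-pump patients will be tested more, so that an off-pump advantage on this outcome would be spurious. The documents do not support that. No section says that transfusion prompts testing. Transplant planning might prompt it, but randomisation balances transplant intent in expectation. Stratification by type of LVAD therapy may balance it by design, if that phrase means bridge or destination use. Case C shows that equally selective testing leaves no difference between arms. The relative risks below 1 in Case A also need a counting rule that the plan does not contain.

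**Conclusion.** The point holds as a conflict over the source of cPRA for secondary outcome 3, with a missing instruction to assay the scheduled samples. Following Determination of Alloantibodies as written would leave post-implant values incomplete and dependent on clinical ordering.

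Bias between arms is possible but not shown. Under the assumed testing rates, the apparent relative risk with no true difference runs from 0.56 to 0.89 if untested patients count as negative. It is 1.0 among the tested if testing is unrelated to sensitization. If testing is selective in the on-pump arm only, the result is 29.7% against 22.0%. All of these rest on testing rates that the documents do not give, and on the 22% background rate applying to both arms.

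Confidence is moderate. The primary outcome is unaffected. The change should be made, because samples that are never assayed, or are unsuitable for the assay, may not be recoverable later.

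**What to change.** Reconcile Study Design and Patients, Blood Collection and Preparation and Determination of Alloantibodies by replacing the whenever-measured rule for this outcome:

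1. Determine cPRA in every randomised patient from the scheduled baseline, 30-day, 6-month and 12-month research draws.
2. Use the one named assay and MFI threshold throughout, with the laboratory unaware of arm.
3. Base outcome 3 on these scheduled values, and list clinically triggered results separately.
4. Treat a missing scheduled value as missing, not as negative, and say so in Statistical Methods.
5. Report the number tested by arm and visit.

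The cost is protocol wording, plus assays for scheduled samples not already tested clinically. No visit or draw is added. The sponsor must also confirm that the collected tube type (K2 EDTA, per Blood Collection and Preparation) suits the assay; the documents do not say.

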The CPB circuit is commonly called "the pump", and it allows the surgeon to perform cardiac surgery on an arrested heart, under optimal visualization. It has been used worldwide in millions of patients; however, the use of CPB during cardiac surgery is associated with complications, such as atrial fibrillation (15, 16), increased pulmonary vascular resistance, stroke and neurocognitive dysfunction (17), renal dysfunction, increased need for blood transfusions, activation of inflammatory mediators, platelet activation, and coagulopathy (18), and about 2% perioperative mortality. Overall, the rates of

these complications are considerable, and these events are largely attributed to the CPB itself and to the aortic cannulation and cross-clamping required with CPB (19).

The patient population that requires LVAD implantation often has evidence of end-organ dysfunction, including liver congestion, renal insufficiency and pulmonary edema. LVAD placement under CPB often exacerbates these pre-existing conditions, resulting in post-operative coagulopathy, bleeding and worsening right heart failure.

Off-pump LVAD surgery

To avoid deleterious consequences of CPB, cardiac surgeons have designed heart stabilizers to allow them to perform cardiac surgery on a beating heart without using CPB. Off-pump cardiac surgery does not require hypothermia, aortic cannulation, or cross-clamping of the ascending aorta. Some studies, including a retrospective analysis of our center data (20), have suggested that off-pump LVAD implantation is associated with a significant reduction in blood transfusions, length of stay in hospital and intensive care unit (ICU) stay (20). Decreased numbers of blood products offer important benefits, especially in the BTT patient population (21). Although the risk of known viral transmission is currently low, stored red blood cells do not function normally, and each unit contains activated inflammatory cells and mediators. These changes cause limited oxygen release, impaired microcirculatory flow, and immune suppression. A number of studies have observed decreased survival associated with transfusions in trauma, coronary artery bypass grafting, and ICU stays. However, these studies were retrospective and had insufficient power to detect moderate but important differences in the incidence of right ventricular dysfunction and allo-antibody formation.

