Based on our surgical team's previous experience with off-pump implantation of Jarvik 2000 (Jarvik Heart, Inc., New York, NY) in animals (22) and humans (23), we started implanting HVADs without CPB in 2011 (11). Our goal was to implant HVAD off-CPB when possible. The decision to implant an LVAD on-CPB was made intraoperatively if patient developed hemodynamic instability during positioning of the heart. We have previously showed that LVAD implantation without the use of CPB helps to minimize post-operative complications without hemodynamic compromise or excessive bleeding during implantation (6).

Left Ventricular Assist Devices and Right Ventricular Dysfunction

Outcomes after LVAD implantation are critically dependent on right ventricular (RV) function. This means that the ability of the RV to keep up with the improved blood flow following LVAD greatly effects how well a person does following surgery. It is understood that a high pulmonary artery (PA) pressure (pressure in the blood vessel that takes blood from the right side of the heart to the lungs) measured before surgery, indicates that a higher risk of right heart failure (RHF) exists after LVAD implantation. Development of RHF in LVAD patients has a direct effect on mortality and is associated with a prolonged ICU stay and hospital admission (24). RHF in LVAD patients leads to increased morbidity and is associated with worse outcomes after cardiac transplantation (25). Despite improvements in surgical and medical management the incidence of RHF after LVAD implantation has plateaued at approximately 20-30% (26). The intra-operative technique used during LVAD implantation may play a role in the preservation of RV function. Cross-clamping and cardioplegia may compromise RV contractility (27).

Left Ventricular Assist Devices and Coagulation-Fibrinolysis Changes during On-Pump and Off-Pump LVAD implantation

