- The patient has peri/postpartum cardiomyopathy, or is a pregnant or lactating woman, or a woman of child-bearing age not using a suitable method of contraception.
- The patient, who in the absence of an ICD (or any implanted device capable of defibrillation), has a history of malignant ventricular arrhythmia or sustained ventricular tachycardia (VT), with sustained VT demonstrated by QRS complexes wider than 120 milliseconds, lasting more than 30 seconds, and with a rate of more than 100 beats per minute on screening ECG or other data supporting this diagnosis.
- Recent history of psychiatric disease, including drug or alcohol abuse, that is likely to impair, in the opinion of the investigator, the subject's ability to comply with protocol-mandated procedures.
- Participation in any other clinical investigation that is likely to confound study results or affect study outcome

DEFINITION OF OUTCOME MEASURES

Primary Outcome Measures

Occurrence of the composite outcome of moderate or severe RV dysfunction (perioperative right heart failure), severe renal dysfunction requiring renal replacement therapy, thrombotic complications or death from any cause within 30 days post LVAD implantation, defined as:

- **Perioperative RV failure** is defined by the INTERMACS scoring as the need for intravenous inotropes for >14 days post-operatively or a right ventricular assist device (RVAD) (37). Right ventricular function will be measured by tricuspid annular plane systolic excursion (TAPSE) values assessed using echocardiography prior to implantation (baseline), 14 (+/- 2 days) days post-implant, 30-days post-implant, 6-months and 1-year post-implant. Additionally, we will collect also hemodynamic evidence of RV dysfunction with: a right-atrial pressure (RAP): pulmonary capillary wedge pressure (PCWP) ratio of ≥ 0.67 .
- **A thrombotic complication** is defined as any thromboembolic event (transient ischemic attack or stroke objectively confirmed with computed tomography) or confirmed pump thrombus as previously done (38). A suspected pump thrombosis event in which a thrombus is confirmed in

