Data will be represented as frequency distributions and percentages. Values of continuous variables will be expressed as mean \pm standard deviation and median with interquartile range, as necessary. Continuous variables will be compared using independent samples t-tests or Wilcoxon rank-sum tests, where appropriate. Categorical variables will be compared by means of χ^2 tests or Fischer's exact test, where appropriate. Hemodynamic variables between ON-pump and OFF-pump procedures will be compared with Kruskal-Wallis tests. To analyze changes in echocardiographic and hemodynamic parameters and laboratory values, McNemar matched-pairs tests will be used to compare preoperative values to postoperative values after matching individual patient data. For all analyses, a $p < 0.05$ will be considered statistically significant. Kaplan-Meier analysis will be used to calculate survival along with a log-rank p value when comparing ON-pump and OFF-pump groups. Actuarial survival at 30-days, 6-months and 1-year post-implantation will be calculated by constructing life tables. All data will be analyzed using STATA 15 software (STATA, 2017, College Station, TX).

EXPECTED RESULTS AND IMPORTANCE OF THE STUDY

As LVADs become a more widely used and accepted treatment option for patients with refractory, end-stage heart failure, it will be necessary to further optimize outcomes and reduce the incidence of postoperative complications. We believe that using off-pump LVAD implantation will significantly reduce transfusion requirements, right ventricular dysfunction and alloantibody formation. We expect that in the off-pump group, there will be less exposure to blood products, which will lead to reduced immunosenzitization. If this research finds that off-pump use can decrease the morbidity and mortality in this patient population, it will greatly influence the manner in which these patients are managed. This would reduce hospitalizations and delays in subsequent transplant planning. This would not only be of great benefit to the patient but would significantly decrease health-care costs.

RISK AND BENEFITS

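### The 80% power for a 30% relative reduction is stated without an on-pump event rate; it requires a 30-day composite rate of about 75%, which nothing in the protocol supports

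*Combined protocol and SAP*

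**What the plan says.** The sample-size justification is a single sentence in Statistical Methods. It opens with "We calculated a sample size of 140 patients (70 in each arm" and then makes its claim for that number, a design "which will provide 80% power to detect a 30% relative risk reduction for the composite primary outcome at 30 days". The sentence gives no control-arm rate, sidedness, test or allowance for dropout.

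Later in the same section, the general analysis text says "Categorical variables will be compared by means of" chi-square or Fisher's exact tests, and that p < 0.05 "will be considered statistically significant". Neither statement is tied to the power calculation.

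Under Primary Outcome Measures, the composite is moderate or severe RV dysfunction, "severe renal dysfunction requiring renal replacement therapy, thrombotic complications or death from any cause within 30 days post LVAD implantation".

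Three Background statements come closest to an event rate:

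- On right ventricular dysfunction, "the incidence of RHF after LVAD implantation has plateaued at approximately 20-30" per cent. This covers one component and is not specific to on-pump implantation.
- On cardiopulmonary bypass, "about 2% perioperative mortality". This refers to cardiac surgery with bypass in general.
- On off-pump LVAD surgery, studies including the centre's own retrospective series are cited as suggesting that "off-pump LVAD implantation is associated with a significant reduction in blood transfusions, length of stay in hospital and intensive care unit (ICU) stay". None of these outcomes is in the composite.

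No rate is given for the composite, for renal replacement therapy or for thrombotic complications.

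**The concern.** For a binary outcome, a relative reduction does not fix the power. The same 30% reduction is an absolute difference of 9 points from a 30% rate and 22.5 points from a 75% rate, and the sample sizes needed differ about fivefold. Without the on-pump rate, the 80% is a claim that no reader can check.

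This sentence is the only basis given for enrolling 140 patients. If the on-pump rate is below the value that the claim silently requires, the chance of detecting a true 30% reduction is below 80%, possibly far below. A reader who trusts the 80% would then take a non-significant result as stronger evidence against a 30% benefit than it is.

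**Working it through.** **Inputs.** From Statistical Methods: n = 70 per arm, power 80%, risk ratio 0.70, level 0.05. Allocation is 1:1 (Study Design and Patients). Sidedness is not stated, so both are tried. Dropout is taken as zero because none is stated. The on-pump rate p is missing, so the stated figure cannot be reproduced forwards. I solve for p instead.

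**Formula (chi-square, pooled normal approximation).** With p1 = p, p2 = 0.70p, d = p1 − p2 and p̄ = (p1 + p2)/2:

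n = [z(α)·√(2p̄(1 − p̄)) + z(0.80)·√(p1(1 − p1) + p2(1 − p2))]² / d²

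**Check at p = 0.75.** Here p2 = 0.525, d = 0.225 and p̄ = 0.6375. The two-sided calculation is:

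n = [1.960 × √0.4622 + 0.8416 × √0.4369]² / 0.225² = (1.3325 + 0.5563)² / 0.0506 = 70.5, rounded up to 71 per arm.

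So the stated design is reproduced only if about three quarters of on-pump patients have an event within 30 days.

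**On-pump rate giving exactly 80% power at 70 per arm**

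| Test | Two-sided | One-sided |
|---|---|---|
| Unpooled z-test | 74.1% | 67.8% |
| Chi-square, pooled approximation | 75.2% | 68.6% |
| Chi-square, exact enumeration | 75.2% | 68.1% |
| Fisher's exact, exact enumeration | 78.0% | 72.3% |

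**Comparison with the protocol's own figures.** Suppose the RV component ran at the quoted 20-30%. For the two-sided chi-square requirement of 75.2%, the other components would have to add a net 75.2 − 30 = 45 to 75.2 − 20 = 55 points. Put another way, 45.2/70 = 65% to 55.2/80 = 69% of patients without RV failure would need renal replacement, a thrombotic event or death within 30 days. Over all tests and both sidednesses, the net addition runs from 67.8 − 30 = 38 to 78.0 − 20 = 58 points.

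**Power at lower rates.** Power = Φ{[d − z(α)·√(2p̄(1 − p̄)/n)] / √([p1(1 − p1) + p2(1 − p2)]/n)}.

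At p = 0.40, p2 = 0.28 and d = 0.12. The two-sided power is Φ[(0.12 − 1.960 × 0.0801)/0.0794] = Φ(−0.465) = 32%.

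The rates below are assumed for illustration, because the documents give none. Chi-square power, detectable fall and n use the pooled approximation; Fisher power is by exact enumeration.

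| On-pump rate | Two-sided chi-square | Two-sided Fisher | One-sided chi-square | Fall detectable with 80% power, two-sided | n per arm for 80% power at a 30% reduction, two-sided |
|---|---|---|---|---|---|
| 30% | 23% | 17% | 34% | to 11.0% (63% reduction) | 367 |
| 40% | 32% | 27% | 44% | to 18.6% (53%) | 244 |
| 50% | 43% | 37% | 56% | to 27.1% (46%) | 170 |
| 60% | 57% | 51% | 69% | to 36.5% (39%) | 120 |

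At a 70% rate, two-sided chi-square power is 72% and one-sided is 82%.

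**Other readings of the sentence.** If 30% meant an absolute reduction of 30 points, only 27 to 42 per arm would be needed at on-pump rates of 35-70%. If 140 were the number per arm, the required on-pump rate would still be about 55%. Neither reading explains the stated figures.

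**The case against.** The strongest reply is that nothing has been shown to be miscalculated. If the sponsor assumed an on-pump rate of about 75%, then 70 per arm is right, and the documents set no upper bound on the composite rate. The 20-30% figure is for right heart failure after LVAD implantation in general, not for on-pump INTERMACS 1-3 patients. The 2% mortality is not an LVAD figure. The phrase about moderate or severe RV dysfunction could be read more widely than the definition that follows it (inotropes for more than 14 days, or an RVAD), which would raise the rate.

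This stands to the extent that the defect is a missing, unsupported assumption rather than a proven arithmetic error, and the table of power at 30-60% is a sensitivity range rather than an estimate of this trial's power. It does not rescue the sentence. A rate of 75% would need to be stated and sourced, and a lower one would make the 80% wrong. The stated RV definition, the exclusion of planned RV support and the restriction of randomization to patients stable on heart positioning also give no reason to expect an unusually high rate.

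Two smaller points are fair. The chi-square answer is 75.2%; the 74.1% belongs to an unpooled z-test. Nothing in the plan says the test is one-sided, so the 68-69% is shown only because sidedness is unstated.

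**Conclusion.** The concern holds. With 70 per arm and a 30% relative reduction, the stated 80% power requires an on-pump 30-day composite rate of about 75% under a two-sided chi-square test, and about 68-78% across the tests and sidedness the text leaves open. No part of the document gives or supports such a rate.

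Below about 75%, two-sided chi-square power is less than stated: 57% at an on-pump rate of 60% and 32% at 40%. Those two rates are my assumptions. The conclusion that the 80% is unsupported does not depend on them. The calculations take equal arms and no dropout. Because this is the only justification for the sample size, on the primary outcome, the sentence needs to be corrected.

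**What to change.** Replace the power sentence with a short paragraph that states:

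1. the assumed on-pump 30-day rate of the composite as defined, and its source (for example the centre's own retrospective series, if it holds these outcomes);
2. the test, and whether the 5% level is one- or two-sided;
3. either the recomputed power for a 30% relative reduction with 140 patients, or the reduction detectable with 80% power. For example, at an assumed 40% on-pump rate with a two-sided test, 70 per arm give 80% power for a fall to about 19%.

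If the sponsor does expect about 75%, it should say so and cite the evidence. Whether 140 remains the target is the sponsor's decision once the rate is on the page.

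The cost is one paragraph and no extra patients, though the stated power will look less favourable if the assumed rate is below about 75%. As a separate reporting point, giving the primary result as a risk ratio and risk difference with 95% confidence intervals would show which reductions the data do and do not exclude.
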